7.2 Rationale

The efficacy and safety of cinacalcet for treatment of sHPT in paediatric patients with ESRD receiving dialysis was evaluated in two randomized controlled studies and one single-arm study ([Sohn et al. 2019](#)). Study 1 was a double-blinded, placebo-controlled study in 43 patients aged 6 to < 18 years who were randomized to receive either cinacalcet (n = 22) or placebo (n = 21). The proportion of patients who achieved the primary endpoint ($\geq 30\%$ reduction from baseline in mean plasma PTH) was 55% and 19% in the cinacalcet and placebo groups, respectively. Study 2 was an open-label study of 55 patients aged 6 to < 18 years who were randomized to receive either cinacalcet in addition to standard of care (SOC) (n = 27) or SOC alone (n = 28) ([Schaefer et al. 2017](#)). The study did not meet its primary endpoint ($\geq 30\%$ reduction from baseline in mean plasma PTH). The proportion that achieved the endpoint was 22% of patients in the cinacalcet plus SOC group and 32% of patients in the SOC group. Study 3 was a 26-week open-label, single-arm safety study of 12 patients aged 8 months to < 6 years who received a single dose of cinacalcet orally or by nasogastric or gastric tube ([Sohn et al. 2019](#)). Serum PTH levels reduced by a median 10.8 and 29.6% at 2- and 8-hours post-dose and returned to baseline by 12-72 hours. Single-dose cinacalcet was well-tolerated with no unexpected safety findings.

Among the paediatric subjects exposed to cinacalcet in the three clinical trials, a total of 19 subjects (24%; 64.5 per 100 subject years) had at least one adverse event of hypocalcaemia; and a fatal outcome was also reported in a patient with severe hypocalcaemia ([Schaefer et al. 2017](#); [Sohn et al. 2019](#); [Warady et al. 2019](#)). The Summary of Product Characteristics (SmPC) states that serum cCa levels and patient compliance during treatment with cinacalcet should be closely monitored ([EMA 2016](#)).

Patients should not be initiated on cinacalcet or increase the dose if non-compliance is suspected.

Following approval of paediatric cinacalcet in Europe, there is a lack of data on real-world use. In addition, there are uncertainties about the incidence of, risk factors for and management of hypocalcaemia among paediatrics in routine clinical practice. As part of the agreement with the EMA following marketing authorization, an observational registry will be conducted to describe real-world utilization of cinacalcet and the incidence and risk factors of hypocalcaemia in a cohort of paediatric patients receiving maintenance dialysis with sHPT in order to inform the management of minimizing this risk of hypocalcaemia in clinical practice.

7.3 Statistical Inference (Estimation or Hypothesis[es])

The objectives of the study are descriptive. No formal hypothesis will be tested.

8. Research Question and Objectives

- What are the characteristics of paediatric patients receiving dialysis who use cinacalcet?
- How is cinacalcet used in paediatric patients?
- How do laboratory values change over time among paediatric cinacalcet users?
- What is the incidence of, risk factors for, and management of hypocalcaemia in paediatric cinacalcet users?

8.1 Primary

In a European cohort of paediatric patients with sHPT on maintenance dialysis and using cinacalcet:

1. To describe patient characteristics
2. To describe how cinacalcet is used
3. To describe laboratory values (PTH, cCa, phosphate and albumin) over time
4. To describe the incidence of hypocalcaemia
5. To describe risk factors associated with time to hypocalcaemia event
6. To describe management of hypocalcaemia

9. Research Methods

9.1 Study Design

This is a non-interventional observational registry of paediatric patients receiving maintenance dialysis with sHPT and using cinacalcet. A patient will receive standard of care treatment as determined by the patient's physician. The overall study design is described in the [Study Schema](#).

Patient eligibility

Paediatric patients on maintenance dialysis with sHPT who use cinacalcet are eligible for study inclusion if they meet study eligibility criteria ([section 9.2.3](#)). Patients eligible for participation include those who have a record of cinacalcet use between 28 August 2017 and 30 June 2023.

Potential patients may be identified via paediatric nephrology networks (eg, European Society for Paediatric Nephrology (ESPN) CKD-MBD Working Group, International Pediatric Dialysis Network (IPDN) or European Study Consortium for Chronic Kidney Disorders Affecting Pediatric Patients (ESCAPE)). Those who meet patient eligibility criteria ([section 9.2.3](#)) will be invited to participate in this registry study. **Patients will not be enrolled until all required signatures have been collected on the informed consent form.**

[figure not shown]
Data collection

Data will be collected from routine medical records and entered into the electronic case report form (eCRF) for the registry database. Baseline data (eg, laboratory parameters PTH, cCa, phosphate, and albumin) in the 90 days prior to index date will be collected. For incident cinacalcet users, this will be 90 days before date of calcimimetic initiation (incident user index date). For prevalent cinacalcet users, this will be from 30 May 2017 to 28 August 2017 (prevalent user index date). Then data will be collected from the index date to the end of the study observational period (31 December 2023) ([section 9.2.5](#)). Chart abstraction will be carried out part retrospectively (ie, data prior to patient enrolment [**enrolment is defined as the date of consent or the date the decision was taken to participate, if consent is not mandated**]) and part prospectively (ie, data **on or** after patient enrolment).

Following enrolment, data will be prospectively collected at 3-month intervals until the end of study follow-up ([Study Schema](#) and [Figure 1](#)). Data available in the preceding 3 months prior to the data collection timepoint will be retrospectively collected. For example, if a patient enrolled on 15 Oct 2019, the next data collection timepoint will be 15 Jan 2020, and all laboratory data values measured between 15 Oct 2019 to 15 Jan 2020 will be collected. If PTH testing was carried out every month, then 3 PTH lab results will be collected. If PTH measurement was carried out only once every three months, then only one value will be collected. The volume of data collected will depend on routine clinical practice at the study site.

However, for countries where a combination of retrospective and prospective data collection methods is not possible, all data will be collected retrospectively before and up to 31 December 2023 (ie, end of study period). Retrospective data will span from 3-months prior to date of cinacalcet initiation (index date) until death, lost-to-follow-up, transfer to another centre that is not participating in this registry, turns age 18-years, withdrawal of consent, or end of the study period (ie, 31 December 2023), whichever comes first.

Figure 1. Data Collection

*For countries where a combination of retrospective and prospective data collection methods is not possible, all data will be collected retrospectively from 31 December 2023.

9.2 Setting and Study Population

The source study population for this study will be comprised of paediatric patients on maintenance dialysis who are prescribed cinacalcet. Potential patients may be identified through paediatric nephrology networks (eg, ESPN CKD-MBD Working Group, IPDN, ESCAPE or other paediatric nephrology networks).

ESPN is a society that promotes research knowledge of paediatric nephrology through teaching, scientific meetings and other methods for the benefit of children with renal disease (<https://espn-online.org/>). The specific CKD-MBD Working Group is focused on providing education and training for management of CKD-MBD in children, perform clinical studies on the topic, and develop appropriate guidelines.

IPDN is a global consortium of paediatric nephrology centres dedicated to the care of children on chronic dialysis (<http://www.pedpd.org/>). Globally, there are 242 institutions in 43 countries participating in the network. In Europe, there are 69 institutions in 18 European Union (EU) countries (Austria, Belgium, Czech Republic, Finland, France, Germany, Hungary, Ireland, Italy, Lithuania, The Netherlands, Poland, Portugal, Romania, Slovenia, Spain, Sweden and the UK) participating in the IPDN. The network

covers approximately 31% of the paediatric dialysis patients in Europe (Schaefer et al. 2012).

ESCAPE is a consortium of European paediatric nephrologists from 33 nephrology centres in Western Europe (<https://www.escapenet.eu/>) dedicated to improve the care of children with kidney diseases (Furth et al. 2018).

9.2.1 Study Period

The study period is anticipated to include data spanning from 30 May 2017 (ie, 90 days prior to 28 August 2017, date of EU marketing authorisation for paediatric cinacalcet, to capture relevant baseline data for prevalent cinacalcet users) to 31 December 2023 (study end date). Eligible patients are those patients who have initiated cinacalcet by 30 June 2023 in order for all patients to have a minimum of 6-month observation data available. **Patients without a history of prior cinacalcet use should have received at least one dose administration at the time of enrolment.**

However, for countries where prospective data collection is not possible, all data will be retrospectively collected for the period spanning 30 May 2017 (if applicable) to 31 December 2023.

9.2.2 Selection and Number of Sites

Approximately 50 to 70 centres across Europe are expected to participate. Eligible sites are centres who are using cinacalcet among paediatric patients on maintenance dialysis. Approximately 1-2 patients are expected to enrol at each site given this special population.

Site selection will be carried out according to normal site evaluation processes. Selection will be based on interest in study participation, and willingness and capacity to comply with protocol and data entry conventions. Sites will be considered active after fulfilling all legal, regulatory and ethical requirements.

9.2.3 Patient Eligibility

9.2.3.1 Inclusion Criteria

- 101 Patients aged ≥ 3 years to < 18 years **at the time of cinacalcet initiation**
- 102 Patients who have provided written informed consent or **appropriate parties have been notified of participation (alive or deceased), where required for access to medical charts**, according to local **laws and regulation** requirements

103 Patients on maintenance dialysis who are diagnosed with sHPT

104 Patients that have a record of cinacalcet use (ie prescription) as per EU marketing authorisation from 28 August 2017 to 30 June 2023

9.2.3.2 Exclusion Criteria

201 Patients who have participated in cinacalcet or etelcalcetide clinical trials

9.2.4 Baseline Period

For 'prevalent' cinacalcet users, the baseline period spans from 30 May 2017 to 28 August 2017 (index date for prevalent cinacalcet users). For 'incident' cinacalcet users, the baseline period is defined as the 90-day period before the date of cinacalcet initiation (index date for incident cinacalcet users). The most proximal laboratory value available prior to index date will be assessed.

9.2.5 Study Follow-up

The registry will record data abstracted from medical charts. Data will be abstracted from the date the patient had a cinacalcet prescription recorded within the study observation period and will continue until death, lost-to-follow-up, transfer to another centre that is not a participating in this registry, turns age 18-years, withdrawal of consent, or end of the study period (ie, 31 December 2023), whichever comes first. Regardless of whether the patient discontinued cinacalcet, follow-up will continue until one of the events described above occurs.

9.3 Variables

9.3.1 Exposure Assessment

All patients enrolled in the study will have had exposure to cinacalcet. A patient's exposure status will be assessed from the medication history recorded in the patient's medical records (and may be identified by the ATC code for cinacalcet: H05BX01). During the observation period, if a patient discontinues cinacalcet treatment during the study period, the availability of treatment data will end on the date in which cinacalcet was first discontinued. However, data abstraction will continue for other parameters (eg, laboratory parameters, PTH, Ca and P) and will be no different from data collection of patients who are using cinacalcet continuously till the end of the study period or till the occurrence of any event that is described in [section 9.2.5](#). Continuous collection will allow capturing data for patients who may have stopped treatment but re-initiated treatment at a later timepoint. For example, patients who discontinued cinacalcet

because of hypocalcaemia and re-start treatment once Ca levels have returned to normal levels.

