Based on the enrolment experience of the IPDN cohort of children and adolescents on maintenance dialysis over the last 10 years, off-label use of cinacalcet was observed among 5 to 10% of the population, or approximately 50 to 100 paediatric patients (IPDN, unpublished). Following EMA approval, use of cinacalcet is expected to double. According to the paediatric cinacalcet clinical trials ([Schaefer et al. 2017](#); [Sohn et al. 2019](#); [Warady et al. 2019](#)), the incidence of hypocalcaemia ranged from 22.7 to 28.0%. Assuming an incidence of 25%, a target sample size of 70 paediatric patients will provide an estimate of hypocalcaemia incidence with a two-sided confidence interval (CI) half-width of 10.1% (ie, two-sided 95% CI: 14.9%, 35.1%) (see [section 9.5](#)).

- **Data Analysis**

There are no formal hypotheses for the study. Descriptive data analyses will be performed. Characteristics of patients who develop and do not develop hypocalcaemia will be described.

Treatment characteristics (cinacalcet and other sHPT medications) will be summarised prior to cinacalcet initiation and after a hypocalcaemia event. PTH, cCa, phosphate and albumin laboratory parameters over time will be summarised.

To describe time-to-event of first hypocalcaemia event, cinacalcet discontinuation and cinacalcet re-initiation, Kaplan-Meier (KM) curves will be calculated.

5. Amendments and Updates

Amendment or Update No.	Date	Section of Study Protocol	Amendment or Update	Reason
1	8 March 2019		See summary changes	
2	23 August 2019		See summary changes	
Superseding Amendment 2	20 September 2019		See summary changes	
3	10 February 2020		See summary changes	

6. Milestones

Milestone	Planned date
Start of data collection	Q4 2019
End of data collection	December 2023
Study progress report	Annually
Annual Report 1	Q4 2020
Annual Report 2	Q4 2021
Annual Report 3	Q4 2022
Registration in the EU PAS register	Q3 2019
Final report of study results	Q4 2024

** These timelines are subject to receiving timely approvals from national competent authorities and ethics committees which may vary by country.

7. Rationale and Background

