 - Dialysis treatment (dialysis vintage at time of cinacalcet initiation, dialysis modality, date, dialysis frequency, dialysis dose, duration, dialysate calcium, ionized calcium before dialysis, switched dialysis modality reason, dialysis discontinuation reason; if dialysis modality is peritoneal dialysis, additional parameters (fill volume, number of cycles, duration of cycle, automated or manual)

For physical measurements (except for Tanner stage) and dialysis treatment variables, data will only be collected every 90 days (+ 30 days) following index date. For all other variables, all data available will be collected if available in the observation period.

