9.7.2.3.2 Description of Patient Characteristics

Demographics and baseline characteristics (specified in [Section 9.3.2](#)) of patients who initiate cinacalcet and patients who develop and do not develop hypocalcaemia will be summarised.

Treatment characteristics (sHPT medications) at time of first cinacalcet use (*'incident cohort'*) or on 28 August 2017 (*'prevalent cohort'*) will be summarised.

PTH, Ca, P and other relevant laboratory parameters will be described by plotting the median and IQR values every month (30 days) or three months (90 days) following index date and following hypocalcaemia event. Data will be presented overall and stratified by levels of control (eg, low, medium or high of Ca values or mild, moderate or severe PTH levels) at baseline or following hypocalcaemia event (mild, moderate and severe hypocalcaemia) to show the longitudinal trajectory of laboratory values.

To describe time-to-event of first hypocalcaemia event (*incident cinacalcet cohort only*), cinacalcet discontinuation (*incident cinacalcet cohort only*) and cinacalcet re-initiation, KM curves will be plotted, and KM estimates will be calculated. Patients will be censored if they had a kidney transplant, parathyroidectomy or experienced one of the follow-up events ([section 9.2.5](#)), whichever comes first. In the time to hypocalcaemia event analysis, patients will also be censored if they discontinued cinacalcet.

To describe risk factors associated with time to first hypocalcaemia event (*incident cinacalcet cohort only*) after cinacalcet initiation, a multivariate Cox model will be used.

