9.7.2.4 Analysis of the Primary Endpoint(s)

Demographics and baseline characteristics (specified in [Section 9.3.2](#)) of patients who initiate cinacalcet and patients who develop and do not develop hypocalcaemia will be summarised.

Treatment characteristics (sHPT medications) at time of first cinacalcet use (*'incident cohort'*) or on 28 August 2017 (*'prevalent cohort'*) will be summarised.

PTH, Ca, P and other relevant laboratory parameters will be described by plotting the median and IQR values every month (30 days) or three months (90 days) following index date and following hypocalcaemia event. Data will be presented overall and stratified by levels of control (eg, low, medium or high of Ca values or mild, moderate or severe PTH levels) at baseline or following hypocalcaemia event (mild, moderate and severe hypocalcaemia) to show the longitudinal trajectory of laboratory values.

To describe time-to-event of first hypocalcaemia event (*incident cinacalcet cohort only*), cinacalcet discontinuation (*incident cinacalcet cohort only*) and cinacalcet re-initiation, KM curves will be plotted, and KM estimates will be calculated. Patients will be censored if they had a kidney transplant, parathyroidectomy or experienced one of the follow-up

events ([section 9.2.5](#)), whichever comes first. In the time to hypocalcaemia event analysis, patients will also be censored if they discontinued cinacalcet.

To describe risk factors associated with time to first hypocalcaemia event (*incident cinacalcet cohort only*) after cinacalcet initiation, a multivariate Cox model will be used.

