9.9 Limitations of the Research Methods

9.9.1 Internal Validity of Study Design

9.9.1.1 Measurement Error(s)/Misclassification(s)

Persistence of medications is quantified by the number of days the medication is available to the patient. This represents a simplified measure, since the definition does not access if the patient takes the medication (ie, compliance/adherence). Nonetheless, in the absence of a valid measure and to maintain consistency and comparability between studies of persistence, the number of days the medication was prescribed to the patient during his/her observation period in this study will be used as a proxy to define persistence.

Hypocalcaemia event is defined by cCa laboratory value and reporting of adverse event due to hypocalcaemia (ie, blood cCa decreased or symptomatic hypocalcaemia). It is possible that hypocalcaemia may be under-reported if a patient did not have both albumin and total serum Ca measured on the same day to calculate cCa. However, we may assume that for those circumstances, hypocalcaemia events (if any occurred) are likely to be asymptomatic. For symptomatic hypocalcaemia events, which result in hospitalisation or medical interventions, these events will be captured as an adverse event.

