9.9.1.2 Information Bias

Information bias is unlikely to affect the findings of this study unless participating sites record exposures and/or outcomes more diligently for patients treated with cinacalcet compared to nephrology centres not participating in the study. It is possible that hospitalised patients may artificially appear to be non-persistent (ie, discontinued) as new prescriptions may not be issued until they return to their nephrology centre. If this is the case, then time-varying analyses would identify hospitalisation as a risk factor, although it should be acknowledged that it would be impossible to determine if this is a true (worsening clinical condition) or artificial effect. However, we anticipate this occurrence to be low as most acute complications are managed in the paediatric nephrology unit where they are normally cared for.

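### Section 9.3.1 ends cinacalcet treatment data at the first discontinuation, in conflict with the protocol's own aim, collection rule and planned analysis of restarts

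*Protocol*

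**What the plan says.** Section 9.3.1 (Exposure Assessment) deals with a child who stops cinacalcet during the study. It says that "the availability of treatment data will end on the date in which cinacalcet was first discontinued". The next sentence opens with a contrast and says that abstraction goes on for other parameters, with laboratory values as the example. The paragraph then gives the reason for going on: "Continuous collection will allow capturing data for patients who may have stopped treatment but re-initiated treatment at a later timepoint". Its illustration is a child who stops because of hypocalcaemia and restarts once calcium has recovered.

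Three other places bear on the same data:

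- Section 9.2.5 keeps patients in follow-up whether or not they discontinue.
- Section 9.3.2 lists cinacalcet use (prescription date, dose, form, change type, reason for change) under an observation period that runs to the end of follow-up. After setting a 90-day schedule for dialysis treatment and most physical measurements, it adds: "For all other variables, all data available will be collected if available in the observation period". Cinacalcet use falls under that rule.
- The abstract announces time-to-event analyses that include "cinacalcet discontinuation and cinacalcet re-initiation, Kaplan-Meier (KM) curves will be calculated". Section 9.7.2.3.2 repeats the plan, ending its list of time-to-event outcomes with "and cinacalcet re-initiation, KM curves will be plotted, and KM estimates will be calculated", and section 9.7.2.4 has the same text.

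**The concern.** A restart is itself treatment data, and it is dated after the first discontinuation. A rule that closes treatment data at the first discontinuation therefore excludes the event that the same paragraph says it wants to capture, and that the analysis sections intend to plot.

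This is not detail that can wait for the statistical analysis plan. It is an instruction about what is abstracted, and an analysis plan cannot supply prescriptions that were never entered. Abstraction is done by site staff, at an expected 50 to 70 centres with about 1 to 2 patients each (section 9.2.2). If some sites follow the cut-off, the registry loses restart dates, restart doses and the reasons for restarting. Those belong to Objective 2 (how cinacalcet is used) and, where the stop was for hypocalcaemia, to Objective 6 (how hypocalcaemia is managed).

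**Working it through.** The protocol gives no figure to reproduce here, so the check sets the rules side by side and follows what each implies for one patient.

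**Notation.** Let D be the date of the first coded discontinuation, R the date of a later restart, and E the end of follow-up under section 9.2.5. By definition R is later than D.

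**What each rule makes observable.**

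1. Section 9.3.1, cut-off sentence read literally: cinacalcet prescriptions are available up to D. A restart at R, after D, is not recorded.
2. Section 9.3.1, purpose sentence: data on patients who stop and re-initiate are to be captured. This needs R.
3. Section 9.3.2: cinacalcet use is collected, with all available data, up to E. A restart at R is recorded whenever R is no later than E.
4. Abstract and sections 9.7.2.3.2 and 9.7.2.4: time to re-initiation is estimated by Kaplan-Meier. This needs R.

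Rule 1 is incompatible with rules 2, 3 and 4.

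**Consequence for the re-initiation curve.** The Kaplan-Meier estimate is the product over event times of (1 − d/n), where d is the number of restarts at that time and n the number still at risk. Under rule 1, d = 0 at every time. Each factor is 1 − 0/n = 1, so the estimated proportion not yet restarted stays at 1 and the cumulative proportion restarting stays at 0, whatever happened in the clinic. The two companion curves are limited to incident users, but no such limit is stated for re-initiation, so both cohorts are concerned.

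**What is not affected.**

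- Time to first hypocalcaemia: section 9.7.2.4 already says "In the time to hypocalcaemia event analysis, patients will also be censored if they discontinued cinacalcet", so it uses no treatment data after D.
- Time to discontinuation: it ends at D.
- Dose changes and temporary withholding before D: section 9.3.2 codes dose change, withheld and discontinued as separate change types, and the cut-off is triggered only by the last.
- Laboratory data and concomitant medication: these continue to E.
- The sample size: section 9.5 rests on the precision of the hypocalcaemia incidence and uses no restart data.

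**Number of patients.** This would be the number of children with a coded discontinuation multiplied by the proportion of them who restart. The protocol gives neither quantity, so it cannot be computed and none is assumed.

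**The case against.** The strongest reply is that the protocol as a whole points the other way. Section 9.2.5 continues follow-up after discontinuation, section 9.3.2 collects all available cinacalcet data to the end of follow-up, and section 9.3.1 itself says restarts are to be captured. The cut-off sentence can also be read mildly, as a remark that no treatment data exist while a child is off the drug. What sites actually enter is governed by sponsor training, the eCRF and its completion guideline, with data review and queries (section 9.6), and none of those documents is shown.

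Much of this stands. A reader might infer that the cut-off is the only instruction on treatment data after a stop. It is not. A reader might also infer that restarts will in fact be lost. The documents do not establish that, and missed entries could be recovered from charts by returning to sites.

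What does not stand is that the sentence is harmless. The word for first discontinuation, and the contrast with other parameters that continue, favour the literal reading over the mild one. Section 9.3.1 is the exposure section, where an abstractor would look for this rule. The change types in section 9.3.2 include no restart, so that section does not clearly override the cut-off.

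Two further supports are tempting and too weak to use. Section 9.9.1.1 measures persistence by "the number of days the medication was prescribed to the patient during his/her observation period", which might be taken to include days after a restart, but it does not mention restarts. Section 9.9.1.2 accepts that a hospitalised child may look as if treatment had stopped, so a record might be closed at a stop that never happened. That adds one hypothetical to another, in a situation the section expects to be uncommon.

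**Conclusion.** The contradiction is real and lies in current protocol text. Read literally, the cut-off leaves zero observable re-initiation events for a planned Kaplan-Meier analysis and removes the stop-and-restart part of Objectives 2 and 6. This rests on one assumption: that a site applies the sentence as written and enters no cinacalcet prescription after a coded discontinuation. The surrounding text shows that this was not the intent, so the point is a faulty collection rule to correct, not a flaw in the analysis method.

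A reader might conclude that Objective 6 as a whole, or the hypocalcaemia results, are compromised. The documents do not support that: the exposure is confined to coded discontinuations followed by a restart. A reader might also measure the loss by the length of follow-up remaining to the study end. That is calendar time, not lost data, and says nothing about how many children restart.

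**What to change.** Replace the cut-off sentence in section 9.3.1 with:

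> Cinacalcet prescription data, including any restart (date, dose, form, reason), are collected to the end of follow-up in section 9.2.5, including after any discontinuation. The first discontinuation ends only the first exposure episode and remains the censoring point for time to first hypocalcaemia.

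Align the eCRF completion guideline if it repeats the cut-off. The change concerns what is recorded, not when treatment should be stopped or restarted.

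The cost is small. Charts are already followed to the end of follow-up for other parameters, so the added work is entering later cinacalcet prescriptions, with a chart look-back for patients already abstracted.
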